7.1 Cisplatin Dose Modifications (Arm 3 only)

7.1.1 Ototoxicity

Grade 3-4 hearing loss/tinnitus is an indication to consider discontinuation of the drug.

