3.0 PATIENT ELIGIBILITY

3.1 Inclusion Criteria

1. Histologically or cytologically confirmed HPV-related stages I-III OPSCC (8th edition of AJCC/UICC Staging Manual) or HPV-related neck node with unknown primary. HPV-related may be defined by p16 IHC stain and/or HPV-ISH or PCR using standard definitions of positive and negative test results. cT1N0 and cT2N0 excluded.
2. Primary tumor that will be resected via a transoral oral approach (conventional surgery, transoral laser microsurgery, transoral robotic surgery)
3. ECOG PS 0-2.
4. Normal organ and marrow function defined as:
 - a. Creatinine clearance > 50 cc/min.
 - b. ANC \geq 1,000/mcL.
 - c. Platelet count \geq 100,000/mcL.
5. At least 18 years of age.
6. Women of childbearing potential and men must agree to use adequate contraception (hormonal or barrier method of birth control, abstinence) prior to study entry and for the duration of participation. Should a woman become pregnant or suspect she is pregnant while participating in this study, she must inform her treating physician immediately.
7. Patient (or legally authorized representative) must be able to understand and willing to sign a written informed consent document.

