5.4 Postoperative Adjuvant Chemotherapy

5.4.1 ARM 1 ONLY - Cisplatin (one dose) + 21 doses of RT

The dose of cisplatin will be given on the same day as one of the initial 5 doses of POART (refer to Section 5.5 for RT dosing).

Recommended procedures for cisplatin therapy are as follows:

1. Antiemetic premedication prior to cisplatin: palonosetron 0.25 mg IVPB, dexamethasone 10 mg IVPB and aprepitant 150 mg IVPB.
2. Hydration consisting of 1L IVF NS (10 meq KCL/L + 8 meq MgSO₄/L) over 60 minutes before and after cisplatin on the day of dosing. 2L IVF NS over 60 minutes on each of the two days following cisplatin dosing.
3. Administration of cisplatin (100 mg/m² IVPB over 60 minutes) on one day only during one of the first 5 doses of radiation.
4. Physical examination will be performed on the day of cisplatin administration and on day 22 (+/- 2) and 36 (+/- 2) after starting radiation therapy.
5. Weight (kg) will be collected weekly during radiation.
6. Documentation of ECOG performance status will be done on the day of cisplatin administration and on days 22 (+/- 2) and 36 (+/- 2) after starting radiation therapy.
7. Documentation of patient symptoms using NCI-CTCAE version 4.0 will be done on the day of cisplatin administration and on days 22 (+/- 2) and 36 (+/- 2) after starting radiation therapy.
8. CBC, BMP and magnesium on the day of cisplatin administration and on days 22 (+/- 2) and 36 (+/- 2) after starting radiation therapy.
9. Patient to complete QOL questionnaire prior to starting radiation (-7/+0) and during the fourth week of radiation (radiation doses 16-21) and 36 (+/- 2) days after starting radiation therapy.
10. OPTIONAL: Patient to receive speech and swallowing assessments prior to starting radiation* and during the fourth week of radiation (radiation doses 16-21) and 2 weeks after completing radiation therapy.
*Modified barium swallow not needed within one week prior to starting radiation.

5.4.2 ARM 2: No Cisplatin. 21 doses of RT only.

Refer to Section 5.5 for RT dosing instructions.

1. Physical examination and weight (kg) will be performed on the first day of radiation therapy and on days 22 (+/- 2) and 36 (+/- 2) after starting radiation therapy.
2. Weight (kg) will be collected weekly during radiation.

3. Documentation of ECOG performance status will be done on the first day of radiation therapy and on days 22 (+/- 2) and 36 (+/- 2) after starting radiation therapy.

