2. Hydration consisting of 1L IVF NS (10 meq KCL/L + 8 meq MgSO₄/L) over 60 minutes before and after cisplatin on the day of dosing. 2L IVF NS over 60 minutes on each of the two days following cisplatin dosing.
3. Administration of cisplatin (100 mg/m² IVPB over 60 minutes) on days 1, 22 (+/- 5), and 36 (+/- 5).
4. Weight (kg) will be collected weekly during radiation.
5. CBC, BMP and magnesium on each day of cisplatin administration (radiation dose 1, 16 (+/- 5) and 26 (+/- 5)).

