7.1.2 Kidney Impairment

Calculated Creatinine Clearance	Percent Dose to Give
≥ 50 mL/min	100%

$< 50 \text{ mL/min}$	0% (withhold treatment for this dose and repeat serum creatinine weekly after additional hydration), then for next chemotherapy dose: If CrCl was already $< 50 \text{ mL/min}$ and is now:	
	$> 40 \text{ but } < 50$	50%
	< 40	0%
	Please note that dose reduction percentage is calculated by taking off from the original dose and not the previous dose.	

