7.1.3 Neutropenia/Thrombocytopenia

Nadir of last course	ANC/Platelets (Day 1 of each cycle)		
	ANC < 500 Plts < 60,000	ANC 500-749 Plts 60,000-99,000	ANC ≥ 750 Plts $> 99,000$
ANC > 500 Plts $> 30,000$	Hold cisplatin	50% cisplatin	100% cisplatin
ANC < 500 Plts < 30,000	Hold cisplatin	Hold cisplatin	50% cisplatin

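### Section 7.1 confines every cisplatin hold to Arm 3, although its same-dose renal hold needs no earlier dose and would fit Arm 1's single 100 mg/m² dose

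*Combined protocol and SAP*

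**What the plan says.** The heading of Section 7.1 is "Cisplatin Dose Modifications (Arm 3 only", and 7.1.1 to 7.1.4 all sit under it.

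- **7.1.2 (kidney).** At CrCl below 50 mL/min the instruction is "0% (withhold treatment for this dose and repeat serum creatinine weekly after additional hydration". Further rows then set the next dose: 50% if CrCl is between 40 and 50, none if it is below 40.
- **7.1.3 (blood counts).** Action depends on "ANC/Platelets (Day 1 of each cycle" and on the nadir of the previous course. In the lowest column (ANC below 500, platelets below 60,000) the entry is "Hold cisplatin" in both nadir rows.
- **5.4.1 (Arm 1).** One 100 mg/m² dose is given "on one day only during one of the first 5 doses of radiation". Laboratory work includes "CBC, BMP and magnesium on the day of cisplatin administration". The list is headed as recommended procedures and gives no action threshold.
- **5.4.3 (Arm 3).** When cisplatin is indicated, the same 100 mg/m² is given "IVPB over 60 minutes) on days 1, 22 (+/- 5), and 36 (+/- 5".
- **3.1 and 5.1.** Entry requires "Creatinine clearance > 50 cc/min", ANC of at least 1,000 and platelets of at least 100,000, from baseline tests done before surgery.
- **5.5.** Radiation may start as late as 56 days after surgery.

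**The concern.** For the same drug, dose and laboratory value, Arm 3 has a fixed hold and Arm 1 has none. Having only one dose does not explain the difference. Arm 3's first dose also has no cisplatin before it and is given in the same early part of radiation, yet it is covered.

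The entry limit does not close the gap. It rests on a measurement taken before surgery, and the dose may follow about two months after the operation. The interim visit in 5.3 repeats the blood count and chemistry, again without a threshold.

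Arm 1 is the primary-endpoint arm of a trial meant to reduce toxicity. Section 1.9 treats a doubling of creatinine as a marker of dehydration or cisplatin toxicity, and 2.2 makes creatinine change in Arm 1 a secondary objective. Two investigators could handle the same dosing-day CrCl of 45 differently. Nothing says whether a dose held in Arm 1 is given later or dropped.

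**Working it through.** **1. Which rules need an earlier dose?**

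| Rule | Needs an earlier dose? | Fits Arm 1's only dose? |
|---|---|---|
| 7.1.1 ototoxicity: consider stopping the drug | Yes, in effect | No |
| 7.1.2 hold at CrCl below 50 | No, acts on the current dose | Yes |
| 7.1.2 rows giving 50% or none | Yes, they set the next dose | No |
| 7.1.3 lowest-count column | No, a hold in 2 of 2 nadir rows | Yes |
| 7.1.3 middle column (50% or hold) and right column (100% or 50%) | Yes, depends on last nadir | No |
| 7.1.4 discretionary hold | No | Yes, but 5.10 already gives general discretion |

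Two fixed holds therefore do not depend on an earlier dose. The renal one is the more plausible in practice: no trial chemotherapy precedes the Arm 1 dose, and entry counts must be well above the 7.1.3 hold values.

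**2. Is there an Arm 1 threshold elsewhere?** Sections 3.1, 5.1, 5.3, 5.4.1, 5.10, 6.1, 7.0 and the calendar in 14.1 contain no numeric cisplatin hold for Arm 1. Section 7.0 covers all arms and points to details that follow, but the only cisplatin details that follow are for Arm 3.

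**3. Would the weekly recheck in 7.1.2 work in Arm 1?** Take day 1 as the first fraction, on any weekday, with uninterrupted treatment. Days 1 to 7 contain exactly five weekdays, so at least five fractions are delivered by day 7. Fraction 5 falls on day 4 to 7, depending on start day and any twice-daily session. The first fraction on day 8 is number 6 with no twice-daily session, 7 with one (5.5), and 7 or 8 with one each week (14.1, footnote 6). A recheck one week after a hold at fraction 1 therefore misses the dosing window unless radiation is delayed, which 7.2 allows.

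**4. How many patients could be affected?** Inputs from 10.2: Arm 1 target 20, with 13 enrolled at December 2019.

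- Remaining: 20 − 13 = 7. This is an upper limit. The alternative cap of 20 further patients in any arm, at the observed Arm 1 share of 13/40 = 32.5%, yields 20 × 0.325 = 6.5.
- The documents give no frequency for meeting a hold. For an assumed rate p, the expected number is 7p and the chance of at least one is 1 − (1 − p)^7.

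| Assumed p | Expected patients | Chance of at least one |
|---|---|---|
| 1% | 0.07 | 1 − 0.99^7 = 6.8% |
| 5% | 0.35 | 1 − 0.95^7 = 30.2% |
| 10% | 0.70 | 1 − 0.90^7 = 52.2% |

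**The case against.** The strongest reply is that Arm 1 is not unprotected. The procedures in 5.4.1 are recommendations. The opening of 5.10, which applies to every arm, calls for stopping protocol therapy when the protocol's constraints are judged harmful to the patient. Section 7.0 requires physician assessment at each scheduled visit and allows that modification may be needed. This stands. A reader might infer that an Arm 1 patient with a CrCl of 45 must receive the full dose; the documents do not say so. What they lack is a trigger. Section 5.10 concerns discontinuation and sets no laboratory value, and 7.0 encourages patients with grade 1-2 events to continue as planned.

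Second, the renal rule is built around a later dose. Arm 3 holds at a CrCl of 45 and may give 50% next time, so the protocol treats that value as a reason to defer, not as a bar. Arm 1 has no next dose, so a hold may become an omission. This also stands: the proposed rule is stricter in effect than Arm 3's, and leaving a single dose to judgment is defensible. It does not explain why the same-day hold covers Arm 3's first dose but not Arm 1's only one.

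Third, the blood-count hold is close to theoretical. That is accepted; it is included only for consistency.

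Fourth, one might read the weekly recheck as always too late. With a radiation delay under 7.2 it need not be.

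**Conclusion.** The point holds as a minor patient-safety clarification. Section 7.1 excludes Arm 1 from a same-dose renal hold that fits it, and no other section supplies a number. The benefit reaches at most 7 further patients under the June 2020 plan; once Arm 1 accrual and dosing are complete, it is a matter of documentation only.

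The chances of 7%, 30% and 52% rest on assumed rates of meeting a threshold. A reader might take them as chances of harm or of a wrong dose. They are not, because a clinician who sees same-day results may hold the dose anyway. Nor does the point affect the primary analysis or the sample size.

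**What to change.** State in 5.4.1 and 7.1 that the hold at CrCl below 50 mL/min also applies to the Arm 1 dose and, for consistency, so do the hold at ANC below 500 / platelets below 60,000 and 7.1.4. Keep the Arm 3 restriction for 7.1.1, the next-dose reductions in 7.1.2 and the nadir-dependent cells of 7.1.3.

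Add for Arm 1: after a hold, with hydration for a renal one, repeat the test before fraction 5. Give the dose within the first 5 fractions if the value has left the hold range; otherwise omit it and continue radiation. The patient stays in Arm 1, since arms are defined by staging and pathology, and the omission is reported under 10.4.1.

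The cost is a few lines of wording and at most one repeat blood draw per held patient, with no new form or analysis. The clinical downside should be acknowledged. An occasional patient with extracapsular extension or a positive margin would receive 42 Gy without cisplatin, the Arm 2 regimen meant for patients without those features. A held first dose in Arm 3 still leaves up to two further doses alongside 60 Gy, possibly at 50% if CrCl is between 40 and 50.

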7.1.2 Kidney Impairment

Calculated Creatinine Clearance	Percent Dose to Give
≥ 50 mL/min	100%

$< 50 \text{ mL/min}$	0% (withhold treatment for this dose and repeat serum creatinine weekly after additional hydration), then for next chemotherapy dose: If CrCl was already $< 50 \text{ mL/min}$ and is now:	
	$> 40 \text{ but } < 50$	50%
	< 40	0%
	Please note that dose reduction percentage is calculated by taking off from the original dose and not the previous dose.	

7.1.3 Neutropenia/Thrombocytopenia

Nadir of last course	ANC/Platelets (Day 1 of each cycle)		
	ANC < 500 Plts < 60,000	ANC 500-749 Plts 60,000-99,000	ANC ≥ 750 Plts $> 99,000$
ANC > 500 Plts $> 30,000$	Hold cisplatin	50% cisplatin	100% cisplatin
ANC < 500 Plts < 30,000	Hold cisplatin	Hold cisplatin	50% cisplatin

7.1.4 Other Grade 2-4 Non-Hematologic AEs

At the discretion of the treating physician, clinical judgement may be used to hold doses of cisplatin if current or interim toxicities are felt to significantly increase the risk of serious toxicity with administration of that dose of cisplatin.

7.2 Radiation Dose Modifications

There are no planned dose modifications or delays for radiation therapy. Delays are allowed at the discretion of the treating physician.

8.0 CORRELATIVE STUDIES

8.1 Tumor Acquisition Protocol

All patients will be strongly encouraged to participate on this companion protocol (HRPO #201102323) for future correlative studies. Tumor samples will be collected in the operating room by trained research personnel, processed and stored according to established protocols.

Correlative studies may be conducted to further determine potential molecular markers of risk in HPV-positive oropharyngeal cancer. These studies may include DNA sequencing for mutational analysis and copy number variations. HPV viral load and integration versus episomal status may also be assessed.

Additionally, gene expression studies, including expression of viral genes, may be conducted on all samples and correlated with other tumor characteristics and outcomes. Future studies may also include the creation of PDX models as well as immunohistochemistry.

8.2 Quality of Life Assessments

QOL will be assessed using the FACT-H&N (Appendix 3), MD Anderson Dysphagia Inventory (Appendix 4), University of Michigan Xerostomia Index (Appendix 5), Scale of Subjective Total Taste Acuity (Appendix 6), and Neck Dissection Impairment Index (Appendix 7) at the following time points:

- Baseline (before the start of any treatment)
- Interim assessment (14-42 days post-surgery)
- Day 1 of radiation (-7/+0 days)
- Day 22 after the start of radiation (Arm 1 & 2 +/- 2 days; Arm 3 +/- 5 days)
- Day 36 after the start of radiation (Arm 1 & 2 +/- 2 days; Arm 3 +/- 5 days)
- 6 weeks after the completion of adjuvant therapy (+/- 1 week)
- 4 months after the completion of adjuvant therapy (+/- 2 weeks)
- 6 months after the completion of adjuvant therapy (+/- 6 weeks)
- 12 months after the completion of adjuvant therapy (+/- 6 weeks)
- 24 months after the completion of adjuvant therapy (+/- 6 weeks)

9.0 REGULATORY AND REPORTING REQUIREMENTS

The entities providing oversight of safety and compliance with the protocol require reporting as outline below.

The Washington University Human Research Protection Office (HRPO) requires that all events meeting the definition of unanticipated problem or serious noncompliance be reported as outlined in Section 9.2.

9.1 Definitions

9.1.1 Adverse Events (AEs)

Definition: any unfavorable medical occurrence in a human subject including any abnormal sign, symptom, or disease.

Grading: the descriptions and grading scales found in the revised NCI Common Terminology Criteria for Adverse Events (CTCAE) version 4.0 will be utilized for all toxicity reporting. A copy of the CTCAE version 4.0 can be downloaded from the CTEP website.

Attribution (relatedness), Expectedness, and Seriousness: the definitions for the terms listed that should be used are those provided by the Department of Health and Human Services' Office for Human Research

Protections (OHRP). A copy of this guidance can be found on OHRP's website:

<http://www.hhs.gov/ohrp/policy/advevntguid.html>

9.1.2 Serious Adverse Event (SAE)

Definition: any adverse drug experience occurring at any dose that results in any of the following outcomes:

- Death
- A life-threatening adverse drug experience
- Inpatient hospitalization or prolongation of existing hospitalization
- A persistent or significant disability/incapacity (i.e., a substantial disruption of a person's ability to conduct normal life functions)
- A congenital anomaly/birth defect
- Any other experience which, based upon appropriate medical judgment, may jeopardize the subject and may require medical or surgical intervention to prevent one of the outcomes listed above

9.1.3 Unexpected Adverse Experience

Definition: any adverse drug experience, the specificity or severity of which is not consistent with the current investigator brochure (or risk information, if an IB is not required or available).

9.1.4 Life-Threatening Adverse Experience

Definition: any adverse drug experience that places the subject (in the view of the investigator) at immediate risk of death from the reaction as it occurred, i.e., it does not include a reaction that, had it occurred in a more severe form, might have caused death.

9.1.5 Unanticipated Problems

Definition:

- unexpected (in terms of nature, severity, or frequency) given (a) the research procedures that are described in the protocol-related documents, such as the IRB-approved research protocol and informed consent document; and (b) the characteristics of the subject population being studied;
- related or possibly related to participation in the research ("possibly related" means there is a reasonable possibility that the incident, experience, or outcome may have been caused by the procedures involved in the research); and

- suggests that the research places subjects or others at a greater risk of harm (including physical, psychological, economic, or social harm) than was previously known or recognized.

9.1.6 Noncompliance

Definition: failure to follow any applicable regulation or institutional policies that govern human subjects research or failure to follow the determinations of the IRB. Noncompliance may occur due to lack of knowledge or due to deliberate choice to ignore regulations, institutional policies, or determinations of the IRB.

9.1.7 Serious Noncompliance

Definition: noncompliance that materially increases risks, that results in substantial harm to subjects or others, or that materially compromises the rights or welfare of participants.

9.1.8 Protocol Exceptions

Definition: A planned deviation from the approved protocol that are under the research team's control. Exceptions apply only to a single participant or a singular situation.

Pre-approval of all protocol exceptions must be obtained prior to the event.

9.2 Reporting to the Human Research Protection Office (HRPO) at Washington University

The PI is required to promptly notify the IRB of the following events:

- Any unanticipated problems involving risks to participants or others which occur at WU, any BJH or SLCH institution, or that impacts participants or the conduct of the study.
- Noncompliance with federal regulations or the requirements or determinations of the IRB.
- Receipt of new information that may impact the willingness of participants to participate or continue participation in the research study.

These events must be reported to the IRB within **10 working days** of the occurrence of the event or notification to the PI of the event. The death of a research participant that qualifies as a reportable event should be reported within **1 working day** of the occurrence of the event or notification to the PI of the event.

9.3 Reporting to the Quality Assurance and Safety Monitoring Committee (QASMC) at Washington University

The PI is required to notify the QASMC of any unanticipated problem occurring at WU or any BJH or SLCH institution that has been reported to and acknowledged by HRPO as reportable. (Unanticipated problems reported to HRPO and withdrawn during the review process need not be reported to QASMC.)

QASMC must be notified within **10 days** of receipt of IRB acknowledgment via email to a QASMC auditor.

9.4 Timeframe for Reporting Required Events

Adverse events will be tracked through the 6 weeks post-end of adjuvant therapy visit. For the purposes of this protocol, adverse events related to the standard of care surgery will not be collected and documented on CRFs.

10.0 STATISTICAL CONSIDERATIONS

10.1 Study Design

This is a three-arm non-randomized Phase II trial. All the enrolled patients will undergo resection of the primary tumor site and involved/at risk regional neck nodes. Patients will be assigned to one of three adjuvant treatments based on the clinical and pathologic staging and the details of the pathology report. 90%, 5%, and 5% of the patients are expected to be in Arm 1, 2, and 3, respectively. The overarching goal is to reduce treatment-related toxicity while maintaining efficacy. Weight loss is a reliable, easily measured and practical surrogate marker of mucosal toxicity. Therefore, the primary objective is to determine the percent weight loss of patients during POAmCRT in Arm 1. The secondary objectives are to evaluate the proportion of PEG tube placements, determine the serum creatinine changes in patients receiving POAmCRT, evaluate the narcotics administration of patients 6 weeks after POAmCRT, document the measures of Quality of Life (QOL) at baseline/during treatment/one year after completion of treatment on all arms, determine the disease recurrence free survival (RFS) at 24 months post-treatment in each arm, and determine progression free survival (PFS) and overall survival (OS).

10.2 Sample Size Calculation

The primary endpoint is percent weight loss from Day 1 of treatment to last day of RT. The sample size calculation is based on the primary endpoint only. Our historical data showed that the mean and standard deviation of percent weight loss during POACRT in patients with HPV-related OPSCC are 7.39% and 5.46%, respectively. The primary hypothesis of this trial is that the percent weight loss of patients in Arm 1 during POAmCRT will be 3.7% (50% reduction). Twenty patients

will have 80% power to detect the percent weight loss difference if assuming the standard deviation of 5.46% using a two-sided one-group t test at the type I error of 5%. We will enroll 24 patients in Arm 1 accounting for 15% drop-out²². We estimate that 14 patients will be enrolled in Arm 2 and 6 patients will be enrolled in Arm 3 for a total of 40 patients.

In December 2019, we reached the 40 patient enrollment mark. However, Arm 1 had enrolled only 13 of the target of 20 patients at that time. In June 2020, we plan to increase enrollment to reach 7 additional patients on Arm 1, or 20 additional patients onto any arm, whichever comes first.

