4.0 REGISTRATION PROCEDURES

Patients must not start any protocol intervention prior to registration through the Siteman Cancer Center.

The following steps must be taken before registering patients to this study:

1. Confirmation of patient eligibility
2. Registration of patient in the Siteman Cancer Center OnCore database
3. Assignment of unique patient number (UPN)

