5.3 Interim Assessment

The interim assessment will include the following tests or procedures and should occur within 14-42 days of surgery:

1. Clinical examination.
2. Documentation of key data from the pathology report: T (1-4) and N (0-3) stage, ECE status (+/-) and extent of ECE (mm), margin status (+/-).
3. Arm assignment (based on pathology data)
4. Documentation of patient symptoms using NCI-CTCAE version 4.0; please note that AEs considered at least possibly related to surgery need not be recorded.
5. Documentation of ECOG performance status.
6. Completion of QOL questionnaires.
7. Documentation of Comorbidity Index.
8. Laboratory evaluations: CBC, BMP, magnesium, PT/PTT.
9. OPTIONAL: Speech and swallowing assessment including MBS and PSS-HN questionnaire.

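### Section 10.2 gives Arm 1 two enrolment targets (24 and 20) and a total of 40 where its arms sum to 44; with 20 enrolled and the plan's own 15% drop-out, power is about 74%, not 80%

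*Combined protocol and SAP*

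**What the plan says.** Section 10.2 (Sample Size Calculation) bases the trial's size on the primary endpoint alone, percent weight loss in Arm 1. Of a sample of 20 it states that they "will have 80% power to detect the percent weight loss difference if assuming the standard deviation of 5.46" (in percent). The test named is a one-group t test, two-sided at the 5% level. It continues: "We will enroll 24 patients in Arm 1 accounting for 15% drop-out". It then estimates that "14 patients will be enrolled in Arm 2 and 6 patients will be enrolled in Arm 3 for a total of 40 patients".

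The following paragraph reports that 40 patients had been enrolled by December 2019, but that "Arm 1 had enrolled only 13 of the target of 20 patients at that time". For June 2020 it says "we plan to increase enrollment to reach 7 additional patients on Arm 1, or 20 additional patients onto any arm, whichever comes first". It does not mention drop-out or power again.

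Section 10.1 (Study Design) gives a different expected allocation: "90%, 5%, and 5% of the patients are expected to be in Arm 1, 2, and 3, respectively".

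**The concern.** All these figures stand in the current text, and they cannot all be right. Arm 1 has an enrolment target of 24 in one paragraph and 20 in the next. The total of 40 fits only the 20. The amended rule counts enrolled patients against 20, which is the number the power calculation needs in the analysis.

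The 80% is the plan's only power statement, and enrolling 24 was what protected it. The amended rule removes that protection and leaves the 80% standing. Enrolment may also end before Arm 1 reaches 20, because 20 further patients in any arm closes accrual. If the Arm 1 result were inconclusive, a reader would judge it against a power that the amended enrolment may not deliver.

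**Working it through.** **Inputs, all from Section 10.2.** Historical mean 7.39 and SD 5.46; hypothesised Arm 1 mean 3.7, so the difference is 7.39 − 3.7 = 3.69 points; one-group t test, two-sided 5%; drop-out 15%; arm sizes 24, 14 and 6; 13 enrolled in Arm 1, plus 7, or 20 in any arm.

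**Method.** Exact power from the noncentral t distribution with n − 1 degrees of freedom and noncentrality (3.69/5.46) × √n = 0.676 × √n.

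**The plan's own figures**

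- n = 20: noncentrality 0.676 × √20 = 3.02, critical value 2.093, power 81.8%. n = 19 gives 79.6%. So 20 is the smallest number that reaches 80%, and the plan's figure reproduces.
- Drop-out: 20 / 0.85 = 23.5, rounded up to 24. This reproduces.
- Total: 24 + 14 + 6 = 44. This does not reproduce; 20 + 14 + 6 = 40 does.
- Amended rule: 13 + 7 = 20 enrolled in Arm 1, and at most 40 + 20 = 60 overall.
- Arm shares: 24/44, 14/44 and 6/44 are 55%, 32% and 14%, against 90%, 5% and 5% in Section 10.1. The observed Arm 1 share was 13/40 = 32.5%.

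**Power by number of evaluable Arm 1 patients**

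| Evaluable | Power for 3.69 points | Difference detectable at 80% power |
|---|---|---|
| 20 | 81.8% | 3.61 |
| 19 | 79.6% | 3.71 |
| 17 | 74.4% | 3.95 |
| 16 | 71.5% | 4.09 |
| 13 | 61.0% | 4.62 |

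Twenty enrolled at 15% drop-out leaves 20 × 0.85 = 17 evaluable on average, hence 74.4%.

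**Power averaged over a binomial number retained**

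| Enrolled in Arm 1 | Drop-out | Average power |
|---|---|---|
| 20 | 0% | 81.8% |
| 20 | 5% | 79.4% |
| 20 | 10% | 76.9% |
| 20 | 15% | 74.1% |
| 24 | 15% | 82.3% |

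**The cap of 20 further patients.** Final Arm 1 size is taken as 13 + min(7, X), with X binomial(20, share). The future Arm 1 share is an assumption.

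| Assumed share | Chance Arm 1 reaches 20 | Power, no drop-out | Power, 15% drop-out |
|---|---|---|---|
| 90% (Section 10.1) | nearly 100% | 81.8% | 74.1% |
| 24/44 (Section 10.2) | 98% | 81.7% | 74.0% |
| 13/40 (observed) | 49% | 79.1% | 71.2% |
| 19% (lower exact 95% limit of 13/40) | 6% | 73.2% | 64.9% |
| 49% (upper exact 95% limit) | 93% | 81.5% | 73.8% |

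At the observed share the cap alone costs 81.8 − 79.1 = 2.7 points. The rest of the fall to 71.2% comes from drop-out.

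**The case against.** The strongest reply is that the 80% is attached to twenty patients and is correct for twenty; the plan never claims it for 17. The change is also disclosed, with dates and counts. Both points are true, but the plan itself expected to need 24 enrolled to analyse 20, and it does not say why that no longer applies.

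A second reply is that 15% may be too high. Section 4.0 requires registration before any protocol intervention, whereas Section 5.3 assigns the arm after surgery, from the pathology data. Patients already counted in Arm 1 are past any losses before assignment, and about four weeks of radiation with weekly weights remain. This stands as a limit: at 5% drop-out, power is 79.4%, close to the stated figure. Even so, 15% is the rate the plan applies to Arm 1 enrolment.

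Third, the planned GEE analysis in Section 10.4.4 keeps patients with some weekly weights, and its stated p-value concerns differences across time points, not a comparison with 7.39%. So the figures above describe the t test that Section 10.2 names, not the power of the GEE model. That also stands.

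Fourth, the 13/40 share assumes that all 40 patients had been assigned an arm by December 2019, which the documents do not say. The cap results at that share are therefore illustrative.

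None of this touches the two targets, the wrong sum or the conflicting arm splits. Reading 20 as evaluable patients fits poorly with text that counts enrolled patients against it.

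**Conclusion.** The concern holds. Section 10.2 states both 24 and 20 as the Arm 1 enrolment target, gives a total of 40 where its arms sum to 44, and conflicts with the allocation in Section 10.1. These inconsistencies need no assumption.

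The loss of power is conditional. If Arm 1 stops at 20 enrolled, power is 74.1% to 81.8% as drop-out runs from 15% to 0%, against 82.3% for the planned 24 at 15%. If the cap binds first it is lower: 71.2% at the observed share with 15% drop-out. These figures take the SD of 5.46 and the 3.69-point difference as given, count each drop-out as wholly lost, and refer to the one-group t test. The derivations of 20 and 24 are sound. The fault is that the amended rule and the total use the evaluable number as the enrolled number.

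**What to change.** In Section 10.2:

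1. Reconcile 24 with 20, and 44 with 40.
2. Say whether the Arm 1 target of 20 means enrolled or evaluable.
3. If it means enrolled, as the wording suggests, state the amended maximum: up to 20 in Arm 1 and up to 60 in total.
4. Replace the single 80% with t-test power by number of evaluable Arm 1 patients for the 3.69-point difference and SD 5.46: 81.8% at 20, 79.6% at 19, 74.4% at 17, 71.5% at 16 and 61.0% at 13. Add that 17 evaluable patients give 80% power for 3.95 points.
5. State that these figures are not the power of the GEE model in Section 10.4.4.

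In Section 10.1, reconcile the 90/5/5 split with the arm sizes in Section 10.2.

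On the enrolled reading the cost is wording only: no extra patients, no change to the accrual cap and no change to the analysis. The stated power becomes less favourable. If the sponsor means 20 evaluable, the limit of 7 additional Arm 1 patients would have to be restated as well, because it allows for no losses.
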